1.0 Research Design

1.1 Purpose/Specific Aims

To evaluate the efficacy and tolerability of 10% povidone-iodine in eliminating nasal carriage of *S. aureus* and MRSA.

A. Objectives

To determine whether a more convenient, single-dose, pre-operative 10% povidone-iodine (PI) application is effective in reducing nasal carriage of *S. aureus* and MRSA.

B. Hypotheses / Research Question(s)

We expect a statistically significant decrease in *S.* aureus/MRSA colonization in nasal cultures taken perioperatively after intervention in patients who received pretreatment with PI as compared to patients who received sterile saline.

1.2 Research Significance

According to some estimates, as many as 25%-30% of healthy individuals in the community have nares colonized with *S. aureus*, while 1%-2.6% have MRSA-colonized nares[1]. This nasal carriage of *S. aureus* and MRSA is a known risk factor for post-operative wound infections in several different types of surgery[2]. Many, if not most infections due to *S. aureus* occur in colonized persons[1]. In implant-based breast reconstruction surgeries for instance, nasal carriers of *S. aureus* are 3 to 6 times more likely than noncarriers to develop nosocomial infections with this pathogen[3]. Similarly, studies have revealed that MRSA nasal colonization may be an independent risk factor for surgical site infection[4]. In a particular study, the MRSA PCR-positive group had a 9-fold increased risk of MRSA surgical site infection compared to the MRSA PCR-negative group, though the former had a low incidence at 1.86%[4]. Coagulase-negative staphylococci (CoNS) are also important etiological agents of post-operative infection[5, 6]. Together, *S. aureus* and CoNS (predominantly *S. epidermidis*, a common denizen of human skin that can colonize nares as well) account for 50-60% of prosthetic joint infections in roughly equal proportions[5, 6].

The agent typically used in assessing the effectiveness of nasal decolonization is mupirocin, which has been shown in some studies to eradicate colonization in up to 92% of post-operative nasal cultures[7]. Randomized controlled trials comparing nasal mupirocin with placebo in general, gynecologic, neurologic, orthopedic, and cardiothoracic procedures have demonstrated that mupirocin reduces the rate of surgical-site infection among known carriers of *S. aureus*[2]. In fact, the American Society of Health-System Pharmacists recommends screening and nasal mupirocin decolonization for *S. aureus*-colonized patients before total joint replacement and cardiac procedures[8]. Likewise, some studies indicate that nasal mupirocin can decolonize CoNS, with only 1.3% of CoNS isolated from the nares of orthopedic surgery patients and 1.6% of samples from prosthetic joint infections displaying some resistance to mupirocin[5].

The mupirocin protocol for nasal decolonization discussed in the literature entails nasal application of mupirocin twice a day for 5 days before surgery[7]. Our end goal is to determine whether a more convenient, single-dose, pre-operative 10% povidone-iodine (PI) application can offer similar if not better surgical site infection results as mupirocin. The first step towards this goal is to evaluate the efficacy and tolerability of 10% povidone-iodine in eliminating nasal carriage of *S. aureus* and MRSA.

1.3 Research Design and Methods

Implement povidone-iodine (10%) pre-operative nasal decolonization for patients undergoing same-day surgery and evaluate efficacy and tolerability of this intervention in eradicating nasal colonization.

HRP-503a - TEMPLATE - Interventional Research Protocol 1.1.21 Protocol Title: Povidone-lodine for nasal decolonization

A. Research Procedures

This will be a prospective single-blinded randomized placebo-controlled trial of two applications of a nasal 10% PI solution used on the intranasal mucosal surfaces of each nostril in the preoperative holding area within 2 hours prior to surgical incision compared with sterile saline using the same technique. Both the PI and sterile saline will be applied by rotating the swab over the intranasal mucosal surface for 15 seconds; this process will be performed twice for both nostrils, using a new swab for each of the 4 applications. 200 subjects will be chosen from a pool of patients arriving at University Hospital, Newark, NJ for outpatient surgery. Inclusion criteria include community-based patients ages 18-80, ASA 1-3 who will be undergoing an outpatient surgery scheduled for at least 1 hour and up to 6 hours duration. Exclusion criteria include pregnancy, allergy to povidone-iodine, infectious indication for surgery or preexisting known infection/wound, known immunocompromised state, use of antibiotics, chemotherapy, or steroids within 1 month prior to surgery. Additionally, patients presenting for surgeries where field avoidance prevents intraoperative access to the nares (e.g., ENT/OMFS/ophthalmology procedures) will be excluded. Patients will be randomly divided into two groups: control (sterile saline) vs. experimental (PI) This will be done via simple randomization using a computer program that assigns patients as they present into either the control or experimental group while maintaining an overall approximately even ratio of subjects in each group.

B. Data Points

Potential subjects will be identified from surgical schedule. Patients will be asked for informed consent in the same-day surgery (SDS) unit. They will be given sufficient time to read the IC document and ask questions. While in the preoperative holding area, patients will be asked to sit upright at a 45-90° angle to prevent drainage into the nasopharynx. All patients will first be swabbed for a nasal swab specimen, once in each nostril. Patients will then receive the appropriate nasal applications depending on the group into which they were sorted: Povidone-Iodine or saline. The tolerability assessment of investigating drug will be done with every subject at the Pre-operating room and PACU by a few criteria as burning/itching, pain, irritation, epistaxis, runny nose, and others. Nasal swab specimen will be obtained by the anesthesiologist intraoperatively 1, 2 and 3 hours after investigational drug application as studies have shown that there a significant decrease in colony-forming units of MRSA even within 1-hour post-treatment [9, 10]. These cultures may be intraoperative or postoperative depending on the length of surgery. There will also be a nasal swab specimen obtained while the patient is in the PACU. Study subjects will be stratified according to age, sex, comorbidities, and ethnicity. Additionally, the type of surgery, duration of surgery (Incision start to incision close), number of surgeons present during the procedure (Include all individuals scrubbed in), postoperative hospital stay length, and intraoperative time (patient in OR to patient out OR) will be used in data analysis. The purpose is to identify variables that increase the incidence of surgical site infection.

C. Study Duration

The study will take approximately 2 years, but chart review may continue up to 4 months after the last patient in the study has their procedure. Chart review of subject's postoperative surgical clinic visits will be performed up to 30 days to monitor for any surgical site infection.

D. Endpoints

The primary study end point is the decrease in S. aureus/MRSA colony forming units (CFU) in nasal swab specimen taken perioperatively after intervention in patients who presented with a positive pre-interventional nasal swab specimen. A secondary endpoint is the presence or absence of surgical site infections at 7 and up to 30-day postop intervals (per retrospective chart review). The review includes an assessment of post-operative infections, complications, and prescribing antibiotics (name, dose, number of days, completing).

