6.0 Data Management Plan

6.1 Data Analysis

We expect a statistically significant decrease in S. aureus/MRSA colonization in cultures taken perioperatively after intervention in patients who received pretreatment with PI as compared to patients who received sterile saline. We assumed that S. aureus/MRSA suppression in 20% of patients would be clinically relevant and that up to 5% of patients may have suppression even without treatment. Using a one-sided alpha of 0.05 and a beta of 80%, we calculated that we would need at least 85 patients in each group for a total of at least 170 patients. A paired t-test will be used to compare preintervention

HRP-503a - TEMPLATE - Interventional Research Protocol 1.1.21

Protocol Title: Povidone-Iodine for nasal decolonization

Protocol Version Date: v5 05.10.23

9/5/2024

nasal culture CFUs to 1- hour postintervention, 2- hour postintervention, and 3-hour postintervention nasal culture CFUs. A 2-sample t test will be used to compare the difference in pre- and post-intervention CFUs between the control and experimental groups at any endpoint. Additionally, mixed regression analysis will be used to determine the effect of the intervention on the CFU counts over all follow-up time points.

The data will be stratified by type of surgery, duration of surgery, and number of surgeons present throughout the procedure. Additionally, the variables age, sex, race, comorbidities, postoperative hospital stay length, and intraoperative time will be used in data analysis. In addition, postoperative surgical site infection (SSI) surveillance for the study participants will be conducted at 7 and 30-day postop intervals.

An intent to treat analysis will include those who are enrolled in the study and meet eligibility requirements for the study. A per protocol analysis will include all eligible patients who complete the assigned study regimen. Completion of the study regimen is defined as 2 applications of sterile saline or PI preoperatively and at least two cultures obtained perioperatively.

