6.4 Reporting Results

A. Individual Subjects' Results

Chart review of the electronic medical record will be used to follow up on patients' visits with their surgeons to determine presence or absence of surgical site infections at 7 and 30-day post-operative intervals.

B. Aggregate Results

Research results will not be shared with patients personally.

C. Professional Reporting

Results from the study will be written into a manuscript for submission into an academic journal and possibly presented at an appropriate medical conference to share results with the scientific community.

D. Clinical Trials Registration, Results Reporting and Consent Posting

A description of this clinical study will be available on ClinicalTrials.gov, as required by U.S. law.

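### SSI is taken from surgical clinic visits that the plan does not require, with no category for patients not assessed, so infections can be missed and SSI rates understated

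*Combined protocol and SAP*

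**What the plan says.** Section 1.3 C names the source and the horizon: "Chart review of subject's postoperative surgical clinic visits will be performed up to 30 days to monitor for any surgical site infection". The same section says that "chart review may continue up to 4 months after the last patient in the study has their procedure".

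Section 1.3 D defines the outcome: "A secondary endpoint is the presence or absence of surgical site infections at 7 and up to 30-day postop intervals", by retrospective chart review. It adds: "The review includes an assessment of post-operative infections, complications, and prescribing antibiotics (name, dose, number of days, completing".

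Section 6.4 A says that review of the electronic record "will be used to follow up on patients' visits with their surgeons to determine presence or absence of surgical site infections", again at 7 and 30 days. Section 6.1 says only that "postoperative surgical site infection (SSI) surveillance for the study participants will be conducted at 7 and 30-day postop intervals", without a method.

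Section 4.7 E lists surgical visit notes among the items drawn from the electronic record, along with diagnosis and concomitant medications. Section 1.3 B gives finding variables that raise SSI incidence as the purpose of collecting the surgical and patient covariates.

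**The concern.** These are outpatients who go home on a surgical follow-up schedule that the trial does not set. The two sections that name which encounters supply SSI confine them to the surgical clinic or the surgeon. The plan requires no visit at either time point, provides for no contact with patients who are not seen, and gives no code for a patient about whom nothing is known.

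Two things can follow. An infection treated in the hospital's own emergency department, or on readmission under another service, can be overlooked although it is in a record the team already opens. And a chart with no surgical visit contains no infection note, so an abstractor offered two values may enter absent.

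Both errors push the SSI rate down. They also matter for the covariate analysis in 1.3 B: if follow-up differs by type of surgery, comorbidity or length of stay, a factor can look related to infection because it is related to being seen.

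**Working it through.** The documents give no SSI rate, expected attendance or SSI power, so there is no figure to reproduce. The main check is to set the sections side by side.

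| Section | SSI source | Timing | Coding |
|---|---|---|---|
| 1.3 C | Surgical clinic visits | Up to 30 days; chart work may run to 4 months after the last procedure | Not stated |
| 1.3 D | Chart review, encounters not named; also complications and antibiotics | 7 and up to 30 days | Two levels |
| 4.7 E | Electronic record, including surgical visit notes | Not stated | Not stated |
| 6.1 | Surveillance, method not named | 7 and 30 days | Not stated |
| 6.4 A | Electronic record, visits with the surgeon | 7 and 30 days | Two levels |

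Wherever an encounter type is specified, it is surgical. No row requires a visit, and none says how to code a patient without one.

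Applied to three patients:

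1. No surgical visit, or only one on day 6: nothing in the named source describes day 30, and the plan does not say what to enter.
2. Infection seen in the emergency department of the same hospital: outside the encounters named in 1.3 C and 6.4 A. It may surface through the antibiotic or complication items in 1.3 D, but the plan does not ensure this.
3. Onset on day 20, first documented on day 33: whether it counts depends on how the 30-day limit in 1.3 C is read.

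**Illustration on assumed values.** Let p be the true 30-day SSI rate and m the share of infections missed and coded absent. Then observed rate = p × (1 − m). With the minimum of 170 patients (1.5 and 4.3 A), the same rate in both arms, and m from 10% to 40%:

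| Assumed p | Observed rate | True events (170 × p) | Observed events |
|---|---|---|---|
| 2% | 1.8% to 1.2% | 3.4 | 3.1 to 2.0 |
| 5% | 4.5% to 3.0% | 8.5 | 7.7 to 5.1 |
| 10% | 9.0% to 6.0% | 17.0 | 15.3 to 10.2 |

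With the 200 subjects named in 1.3 A, event counts rise by 200/170 = 1.18 and the rates do not change.

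**Between arms.** With equal m, the risk ratio is p₁(1 − m) / [p₂(1 − m)] = p₁/p₂, so it is unchanged. Two-sided power at 85 per group for 5% versus 2.5% is 13.5% with full ascertainment and 12.5% to 9.6% with m of 10% to 40%. It is low either way.

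**Between covariate groups.** Take two types of surgery with the same true rate of 5%, but m = 10% in one and 40% in the other. The observed rates are 5% × 0.9 = 4.5% and 5% × 0.6 = 3.0%. The apparent ratio is 1.5 with no true difference.

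Here m is the share of infections missed, not the share of patients unseen. If infected patients are more likely to return to their surgeon, m is smaller than the share of patients unseen.

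**The case against.** The strongest reply is that the plan is silent here and not wrong. A two-level endpoint does not forbid missing values, and no section tells abstractors to enter absent for an unseen patient. Section 1.3 D has them look at complications and antibiotics, 4.7 E draws on the wider electronic record, and the surveillance in 6.1 is not confined to clinic visits. The 30-day limit may describe the outcome period, in which case the 4-month allowance leaves room to read later notes. SSI is secondary, 1.5 and 6.1 name tests only for CFU counts, and 1.2 presents the trial as a first step concerning nasal carriage.

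Much of this stands, and it rules out several stronger readings that a reader might infer:

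- *Unseen patients are recorded as infection-free.* The documents contain no coding rule, so they support only that such patients can default to absent.
- *The window is tied to visit date, so the 4 months go unused.* The wording in 1.3 C is ambiguous and does not establish this.
- *The gap creates a false difference between arms.* That needs attendance to differ by arm. In a randomised, single-blinded trial the documents give no reason to expect it.
- *SSI is the only safety outcome after discharge.* Section 1.3 D also reviews complications and antibiotic prescribing.
- *The benefit statement in 4.7 F rests on these data.* It is a prospective statement of possible benefit and does not depend on this trial's SSI results.

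The reply does not close the gap. Section 1.3 D says what is abstracted but not from which encounters, and the two sections that do name encounters confine them to surgical visits. Nothing separates a patient known to be free of infection from one about whom nothing is known.

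**Conclusion.** The concern holds in a limited form. As written, SSI ascertainment is passive, confined to surgical visits wherever the source encounters are named, and without a rule for patients not seen. Infections recorded elsewhere in the same hospital can be missed and unseen patients can be counted as absent. The bias is downward for SSI rates, and the covariate analysis in 1.3 B could be distorted even if loss is equal between arms.

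The size cannot be determined from the documents. The illustrative figures rest on assumed rates of 2% to 10% and assumed losses of 10% to 40%, and on missed infections being coded absent. With roughly 3 to 9 expected events at assumed rates of 2% to 5% in 170 patients, one or two missed infections would be a visible share. The between-arm risk ratio is not shown to be biased, and the primary CFU endpoint is untouched. This is a worthwhile and inexpensive improvement to a secondary endpoint, not a threat to the trial's main conclusion.

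**What to change.** Amend 1.3 C, 1.3 D, 6.1 and 6.4 A so that they state one rule:

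1. **Source.** Review every encounter in the hospital's electronic record: surgical clinic, emergency department, readmission, wound cultures and antibiotic orders.
2. **Timing.** Define SSI by onset on or before day 7 and on or before day 30. Use later notes, within the 4-month chart-review period already allowed, to identify infections that began in time.
3. **Coding.** Use present, absent or not assessed. Absent at day 30 should need an encounter at or after day 30, or another cut-off fixed in advance, with no SSI noted; set the matching rule for day 7. Do not count not assessed as absent.
4. **Reporting.** Give the number assessed per arm. A present code needs only one note while an absent code needs a late encounter, so the rate among those assessed will tend to run high. Showing events over all analysed patients beside it makes the range visible.

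The cost is protocol wording, one more category on the abstraction form, slightly more reading in records already opened, and an SSI denominator smaller than the number enrolled. No new visits or patients are needed. Care at other hospitals would still go uncaptured, and the report should say so as a limitation.

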1.5 Sample Size Justification

We assumed that *S.* aureus/MRSA suppression in 20% of patients would be clinically relevant and that up to 5% of patients may have suppression even without treatment. Using a one-sided alpha of 0.05 and a beta of 80%, we calculated that we would need at least 85 patients in each group for a total of at least 170 patients. A paired t-test will be used to compare preintervention nasal culture CFUs to 1- hour post application, 2- hour post application, and 3-hour post application, nasal culture CFUs. A 2-sample t test will be used to compare the difference in pre- and post- intervention CFUs between the control and experimental groups at any endpoint. Additionally, mixed regression analysis will be used to determine the effect of the intervention on the CFU counts over all follow-up time points.

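### The 85 per group counts enrolled patients, but the primary endpoint exists only in baseline-positive patients, and the denominator of 20% versus 5% is not stated

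*Combined protocol and SAP*

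**What the plan says.** Section 1.3 D restricts the primary endpoint to CFU decrease "in patients who presented with a positive pre-interventional nasal swab specimen". Section 1.5, repeated in 6.1, assumes that "suppression in 20% of patients would be clinically relevant and that up to 5% of patients may have suppression even without treatment" and concludes that "we would need at least 85 patients in each group for a total of at least 170 patients", at one-sided alpha 0.05 and 80% power (printed there as beta). Section 4.3 gives the same figure as the total number of subjects and judges 170 feasible from same-day surgery volume and broad eligibility. Section 1.3 A has a different total: "200 subjects will be chosen from a pool of patients arriving at University Hospital, Newark, NJ for outpatient surgery".

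Neither 1.3 A nor 4.1 C requires a positive nasal culture. Under 1.3 B every patient is swabbed and then treated. Under 1.8 the swabs go by overnight courier to an outside laboratory.

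The only carriage figure is background text in 1.2: "as many as 25%-30% of healthy individuals in the community have nares colonized with" S. aureus.

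The planned analyses in 1.5 and 6.1 are on CFU, not on a suppression rate: paired t tests within patients, then "A 2-sample t test will be used to compare the difference in pre- and post- intervention CFUs between the control and experimental groups", and "mixed regression analysis will be used to determine the effect of the intervention on the CFU counts over all follow-up time points". Section 6.1 also defines an intent-to-treat set (enrolled and eligible) and a per-protocol set. It ties neither to the baseline-positive population of 1.3 D.

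**The concern.** The sample size and the primary endpoint refer to different populations. A patient with a negative baseline swab adds to the 170 but has no positive count to reduce. The baseline culture result is not available before treatment, so carriers cannot be selected at entry. The number who can contribute therefore depends on carriage, which does not enter the calculation.

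The 20% and 5% are given only as shares of patients. Read as rates in carriers, they leave the comparison used for sizing far below its stated power. Read as shares of everyone enrolled, they leave it well powered, but on a large effect in carriers that nobody has written down. A reader cannot tell which applies, so the stated 80% cannot be interpreted for the primary endpoint. With no link between the analysis sets in 6.1 and the population in 1.3 D, the set for the primary CFU analysis is also open to argument once data are in hand.

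**Working it through.** **Inputs.** Rates 0.05 and 0.20, one-sided alpha 0.05, power 80%, 85 per group (1.5); 200 enrolled, taken as 100 per group (1.3 A). Carriage of 25-30% is from 1.2 and is an assumption for this population.

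**The plan's own figure.** Pooled-variance formula with mean rate 0.125:

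n = [1.645 × √(2 × 0.125 × 0.875) + 0.842 × √(0.05 × 0.95 + 0.20 × 0.80)]² / 0.15² = (0.7693 + 0.3834)² / 0.0225 = 59.05, so 60 per group.

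The stated 85 is not reproduced. A continuity correction gives 72 and a two-sided test 76. The point here does not depend on where 85 came from. With all 85 evaluable, power for 20% versus 5% would be 91%.

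**Evaluable patients per arm** = enrolled × carriage / 2.
- 170 enrolled: 170 × 0.25 / 2 = 21.25 (21); 170 × 0.30 / 2 = 25.5 (26).
- 200 enrolled: 200 × 0.25 / 2 = 25; 200 × 0.30 / 2 = 30.
- Totals: about 43 to 60 patients.

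**Reading A: 20% and 5% are rates in carriers.** Power = Φ{[0.15√n − 0.7693] / 0.4555}. At n = 21: (0.6874 − 0.7693) / 0.4555 = −0.180, so 0.429. At n = 30: (0.8216 − 0.7693) / 0.4555 = 0.115, so 0.546. The plan names no binary test, so exact enumeration is shown as well.

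| Carriers per arm | Pooled formula | Exact, z test | Exact, Fisher | Rate detectable against 5%, 80% power (pooled) |
|---|---|---|---|---|
| 21 (170 enrolled, 25%) | 43% | 46% | 24% | 35% |
| 26 (170 enrolled, 30%) | 50% | 54% | 35% | 31% |
| 25 (200 enrolled, 25%) | 48% | 52% | 33% | 32% |
| 30 (200 enrolled, 30%) | 55% | 59% | 36% | 29% |

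The required 60 carriers per arm would need 60/85 = 71% of 170 enrolled, or 60/100 = 60% of 200, to be baseline-positive. Sensitivity by the pooled formula: 37-41% power at 20% carriage (17-20 per arm) and 59-65% at 40% (34-40 per arm).

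**Reading B: 20% and 5% are shares of all enrolled.** Comparing everyone enrolled, pooled-formula power is 91% at 85 per group and 95% at 100. Only carriers can be suppressed, so the implied rates in carriers are 0.20/0.25 = 80% versus 0.05/0.25 = 20%, or 0.20/0.30 = 67% versus 0.05/0.30 = 17%. Compared in carriers only, power is 98% or more by all three methods.

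**CFU t test.** Power cannot be computed without a difference and an SD. In SD units (noncentral t, 80% power, one time point), 30 and 21 per arm detect 0.65 and 0.78 SD one-sided at 0.05, or 0.74 and 0.89 SD two-sided. Section 1.5 attaches one-sided alpha to the sample size, not to this test, so either is an assumption.

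**The case against.** The strongest objection is that no binary test is planned. The primary analysis is on CFU, with repeated measurements, and a continuous analysis may have quite different power from a 20% versus 5% comparison. That stands. A reader might infer from the table that the trial has about an even chance of succeeding on its primary endpoint. The documents do not support this, because they give nothing from which CFU power can be derived. The figures describe only the comparison that the plan itself used for sizing.

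Second, the denominator may be all enrolled patients, and then the trial is amply powered. That is possible. The background reports that mupirocin can "eradicate colonization in up to 92% of post-operative nasal cultures", so 67-80% in carriers is not out of reach. But that is another agent, the plan does not cite it as a basis, and section 1.4 offers no preliminary data.

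Third, carriage may differ from 25-30%, which describes healthy community members. True, but at 40% carriage Reading A still falls short of 80%.

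Fourth, the normal approximation is rough here: 21 controls at 5% give about one expected event. That stands, and is why a range across methods is needed. No method exceeds 60% at 21-30 per arm.

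Fifth, 1.3 D does name the primary population, so it would be wrong to say that the plan never defines it. The gap is that 6.1 does not connect its analysis sets to it.

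A reader might also set 0.65-0.78 SD against the 0.35-0.38 SD detectable one-sided with 85-100 per arm, and conclude that restriction to carriers roughly doubles the detectable CFU difference. That holds only if every enrolled patient were baseline-positive with the same SD. Including real non-carriers would change both the mean difference and the SD.

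**Conclusion.** The point holds as a mismatch between the population used for sizing and the population of the primary endpoint, together with an unstated denominator. It is not an arithmetic slip. Under assumed carriage of 25-30%, about 21-26 per arm (170 enrolled) or 25-30 per arm (200 enrolled) are evaluable.

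If the rates apply to carriers, power for the binary comparison is 43-50% or 48-55% respectively by the pooled formula, 46-59% by the exact z test and 24-36% by Fisher, instead of 80%. If they are shares of all enrolled, it is 91-95% comparing everyone, or about 98% or more in carriers, resting on an unstated effect in carriers.

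The documents do not support the flat statement that the trial is underpowered: that follows only on Reading A, and only for a comparison that is not the planned analysis. They do support saying that the stated power cannot be interpreted for the primary endpoint and has to be restated.

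**What to change.** 1. In 1.5, 4.3 and 6.1, state the expected number of baseline-positive patients (about 43-60 of 170-200, with carriage labelled as assumed) and the denominator of the 20% and 5%. Restate power to match, name the test, and say that it refers to the binary comparison.
   - If carriers: about 43-55% by the pooled formula (24-59% across methods), with a detectable rate of about 29-35% against 5% at 80% power.
   - If all enrolled: 91-95% comparing all enrolled, with the implied 67-80% versus 17-20% in carriers stated and justified.
2. For the CFU t test, give the assumed difference and SD. Failing that, state that 21-30 per arm detects about 0.65-0.78 SD (one-sided 0.05) or 0.74-0.89 SD (two-sided 0.05) at 80% power at a single time point. Any comparison with 85-100 per arm should say that it assumes all enrolled are baseline-positive with the same SD.
3. In 6.1, link the analysis sets to 1.3 D: the primary CFU analysis uses all randomised patients with a positive baseline swab, analysed as randomised.

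The cost is wording in three sections and possibly a less favourable stated power. No added enrolment is needed for the statement to be true. Reaching 80% power for 20% versus 5% in carriers would take about 120/0.30 = 400 to 120/0.25 = 480 enrolled, which is a separate decision for the investigator.
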